5.2. Exclusion Criteria

Participants are excluded from the study if any of the following criteria apply:

Medical Conditions

- 1. Have DM according to Japanese Clinical Practice Guideline for Diabetes 2019 (Araki et al. 2020), history of ketoacidosis or hyperosmolar state/coma, or laboratory evidence of diagnostic of DM during screening including either HbA1c ≥6.5%, or glucose levels (fasting glucose or OGTT 0-hour ≥126 mg/dL and/or OGTT 2-hour glucose ≥200 mg/dL);
 - a. Diagnosis of DM
 - i. Both glucose level and HbA1c meets diabetic type criteria
 - ii. Only glucose level meets diabetic type criteria at Visit 1
 - With typical symptoms of DM or definite diabetic retinopathy
 - Without typical symptoms of DM or definite diabetic retinopathy, re-exam at Visit 2 and
 - o Both glucose level and HbA1c meet diabetic type criteria
 - o Only glucose level meets diabetic type criteria
 - o Only HbA1c meets diabetic type criteria
 - iii. Only HbA1c meets diabetic type criteria, re-exam at Visit 2 and
 - Both glucose level and HbA1c meet diabetic type criteria
 - Only glucose level meets diabetic type criteria
 - Only HbA1c meets diabetic type criteria
 - b. Prior treatment (within 3 months prior to Visit 1) with DPP-4 inhibitors, oral GLP-1 RA, or any injectable therapy for T2DM
- 2. Alcohol consumption >7 units (140 g of pure alcohol)/week for women and >10.5 units (210 g of pure alcohol)/week for men (JSG 2014)
- 3. Evidence of acute or chronic liver disease other than NAFLD
 - a. Alcoholic liver disease
 - b. Hepatitis B as defined by presence of hepatitis B surface antigen (HBsAg)
 - c. Hepatitis C as defined by presence of hepatitis C virus (HCV) ribonucleic acid (RNA) or positive hepatitis C antibody (anti-HCV). Participants treated for hepatitis C (and diagnosed as cured) must be RNA negative for at least 3 years prior screening in order to be eligible for the study
 - d. Primary biliary cirrhosis as defined by the presence of at least 2 of the following:
 - i. Biochemical evidence of cholestasis based mainly on alkaline phosphatase (ALP) elevation

- ii. Presence of anti-mitochondrial antibody
- iii. Historical evidence of nonsuppurative destructive cholangitis and destruction of interlobular bile ducts
- e. Evidence of autoimmune liver disease as defined by compatible liver histology
- f. Primary sclerosing cholangitis
- g. Current drug-induced liver disease as defined on the basis of typical exposure and history
- h. Suspected or proven liver cancer
- Have acute or chronic hepatitis, signs and symptoms of any other liver disease other than NAFLD, or any of the following, as determined by the central laboratory during screening:
 - alanine aminotransferase (ALT) level $>3.0\times$ the upper limit of normal (ULN) for the reference range

or

· ALP level $>1.5\times$ the ULN for the reference range

or

 total bilirubin (TBL) level >1.2× the ULN for the reference range (except for cases of known Gilbert's Syndrome)

Note: Participants with NAFLD are eligible to participate in this trial if their ALT level is $\leq 3.0 \times$ the ULN for the reference range.

- 4. Have a self-reported change in body weight >5 kg within 3 months prior to screening
- 5. Have or plan to have endoscopic and/or device-based therapy for obesity or have had device removal within the last 6 months

Examples:

- mucosal ablation
- gastric artery embolization
- · intragastric balloon
- · duodenal-jejunal bypass sleeve endoluminal liner
- 6. Have renal impairment measured as estimated glomerular filtration rate (eGFR) <30 mL/min/1.73 m², calculated by Japanese Society of Nephrology coefficient-modified Chronic Kidney Disease-Epidemiology equation as determined by central laboratory during screening
- Have a known clinically significant gastric emptying abnormality (for example, severe gastroparesis or gastric outlet obstruction) or chronically take drugs that directly affect GI motility
- 8. Have had a history of chronic or acute pancreatitis
- 9. Have thyroid-stimulating hormone outside of the range of 0.4 to 6.0 $\mu IU/mL$ at screening visit

Note: Participants receiving treatment for hypothyroidism may be included, provided their thyroid hormone replacement dose has been stable for at least 3 months.

Note: Thyroid-stimulating hormone values above the normal range can, in some participants, suggest subclinical hypothyroidism. If, in the investigator's opinion, the participant has subclinical hypothyroidism and may require initiation of thyroid hormone replacement during the course of the study, the participant should be excluded from the study.

- 10. Have obesity induced by other endocrinologic disorders (for example, Cushing's Syndrome) or diagnosed monogenetic or syndromic forms of obesity (for example, Melanocortin 4 Receptor deficiency or Prader Willi Syndrome)
- 11. Have a history of significant active or unstable major depressive disorder or other severe psychiatric disorder (for example, schizophrenia, bipolar disorder, or other serious mood or anxiety disorder) within the last 2 years

Note: Participants with major depressive disorder or generalized anxiety disorder whose disease state is considered stable for the past 2 years and expected to remain stable throughout the course of the study, in the opinion of the investigator, may be considered for inclusion if they are not on excluded medications

- 12. Have any lifetime history of a suicide attempt
- 13. Have a Patient Health Questionnaire-9 (PHQ-9) score of 15 or more at Visit 1 or 3, prior to randomization
- 14. On the Columbia-Suicide Severity Rating Scale (C-SSRS) at Visits 1 or 3, prior to randomization:
 - a. a "yes" answer to either Question 4 (Active Suicidal Ideation with Some Intent to Act, Without Specific Plan)

or

b. a "yes" answer to Question 5 (Active Suicidal Ideation with Specific Plan and Intent) on the "Suicidal Ideation" portion of the C-SSRS

c. a "yes" answer to any of the suicide-related behaviors (Actual Attempt, Interrupted Attempt, Aborted Attempt, Preparatory Act or Behavior) on the "Suicidal Behavior" portion of the C-SSRS

and

- d. the ideation or behavior occurred within the past month
- 15. Have any of the following cardiovascular conditions within 3 months prior to randomization:
 - · acute myocardial infarction
 - cerebrovascular accident (stroke)
 - · unstable angina
 - · hospitalization due to congestive heart failure
 - · uncontrolled hypertension (systolic blood pressure above or equal to 160 mmHg and/or diastolic blood pressure above or equal to 100 mmHg)
- 16. Have New York Heart Association Functional Classification IV congestive heart failure
- 17. Have a serum calcitonin level (at Visit 1) of 35 ng/L or more, as determined by central laboratory at Visit 1

- 18. Have a family or personal history of medullary thyroid carcinoma or Multiple Endocrine Neoplasia Syndrome type 2
- 19. Have a history of an active or untreated malignancy or are in remission from a clinically significant malignancy (other than basal- or squamous-cell skin cancer, in situ carcinomas of the cervix, or in situ prostate cancer) for less than 5 years
- 20. Have any other condition not listed in this section (for example, hypersensitivity or intolerance) that is a contraindication to GLP-1R agonists
- 21. Have a history of any other condition (such as known drug or alcohol abuse, diagnosed eating disorder, or other psychiatric disorder) that, in the opinion of the investigator, may preclude the participant from following and completing the protocol
- 22. Have had a transplanted organ (corneal transplants [keratoplasty] allowed) or awaiting an organ transplant
- 23. Have any hematological condition that may interfere with HbA1c measurement (for example, hemolytic anemias, sickle cell disease)

Prior/Concomitant Therapy

- 24. Have current or potential needs of glucocorticoid therapy:
 - a. Are receiving or have received within 3 months prior to screening chronic (>2 weeks or 14 days) systemic glucocorticoid therapy (excluding topical, intraocular, intranasal, intra-articular, or inhaled preparations)
 - b. Have evidence of a significant, active autoimmune abnormality (for example, lupus or rheumatoid arthritis) that has required (within the last 3 months) or is likely to require, in the opinion of the investigator, concurrent treatment with systemic glucocorticoids (excluding topical, intraocular, intranasal, intra-articular, or inhaled preparations) during the study
- 25. Have current or history of (within 3 months prior to randomization) treatment with medications that may cause significant weight gain, including but not limited to: tricyclic antidepressants, atypical antipsychotics and mood stabilizers for example:
 - imipramine
 - amitriptyline
 - mirtazapine
 - paroxetine
 - phenelzine
 - chlorpromazine
 - thioridazine
 - clozapine
 - olanzapine
 - valproic acid and its derivatives
 - lithium

Note: Selective serotonin reuptake inhibitors other than paroxetine are permitted.

- 26. Have taken within 3 months prior to randomization, medications (prescribed, imported or over the counter) or alternative remedies intended to promote weight loss or may cause weight reduction. Examples include, but are not limited to:
 - Sanorex® (mazindol)
 - Bofu-tsusho-san® (Chinese herbal medicine)
 - Saxenda® (liraglutide 3.0 mg)
 - Xenical® (orlistat)
 - Meridia® (sibutramine)
 - Acutrim® (phenylpropanolamine)
 - Adipex® (phentermine)
 - BELVIQ® (lorcaserin)
 - Qsymia[®] (phentermine/topiramate combination)
 - Contrave® (naltrexone/bupropion)

Note:

- Use of metformin or any other glucose-lowering medication, whether prescribed for polycystic ovary syndrome or diabetes prevention is not permitted.
- Use of semaglutide that may cause significant weight reduction is not allowed within 12 months prior to randomization.
- 27. Have started implantable or injectable contraceptives (such as Depo-Provera®) within 18 months prior to screening

Prior/Concurrent Clinical Study Experience

- 28. Are currently enrolled in any other clinical study involving an investigational product (IP) or any other type of medical research judged not to be scientifically or medically compatible with this study
- 29. Within the last 30 days prior to screening, have participated in a clinical study and received treatment, whether active or placebo. If the study involved an IP, 5 half-lives or 30 days, whichever is longer, should have passed
- 30. Have previously completed or withdrawn from this study or any other study investigating tirzepatide

Other Exclusions

- 31. Are investigator site personnel directly affiliated with this study and/or their immediate family. Immediate family is defined as a spouse, legal partner, parent, child, or sibling, whether biological or legally adopted
- 32. Are Eli Lilly and Company (Lilly) employees

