Study GPHZ is a Phase 3, multicenter, randomized, placebo-controlled, double-blinded study to evaluate the safety and efficacy of tirzepatide 10 mg and 15 mg administered subcutaneously once weekly compared with placebo when used in conjunction with a reduced-calorie diet and increased physical activity for weight management, in participants who have

- \cdot A BMI of 27 kg/m² or greater and less than 35 kg/m² and at least 2 obesity-related health problems; OR
- · A BMI of 35 kg/m² or greater and at least 1 obesity-related health problem.

Obesity-related health problems are defined as IGT, hyperlipidemia, or NAFLD.

All participants will undergo a 4-week screening period and a 72-week treatment period including a 20-week dose escalation. The safety follow-up period will be 4 weeks.

Study participants will be randomized in a 1:1:1 ratio to tirzepatide 10 mg QW, tirzepatide 15 mg QW, or placebo QW, stratified by

- baseline IGT (yes or no)
- baseline hyperlipidemia (yes or no)
- baseline NAFLD (yes or no), and
- sex (male, female).

Disclosure Statement:

This is a parallel group-treatment study with 3 arms that is participant- and investigator-blinded.

[figure not shown]
Number of Participants:

Approximately 348 participants will be screened to achieve 261 randomly assigned to study intervention for an estimated total of 87 evaluable participants per intervention group.

Intervention Groups and Duration:

All doses will be subcutaneously administered once-weekly using single-use pens. The starting dose of tirzepatide will be 2.5 mg QW (or matching placebo) for 4 weeks, then the dose will be increased by 2.5 mg (or matching placebo) every 4 weeks: 2.5 to 5 to 7.5 to 10 mg for those randomized to 10 mg, and continuing to 12.5 to 15 mg for those randomized to 15 mg.

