1.3. Schedule of Activities

Table 1. Study Period I -Screening and Randomization

Activity Screening		ening	Randomization	Comments
Visit number	1	2	3	
Week of treatment	-4	-2	0	
Allowable deviation (days)	NA	-7/+3	-3/+7	The visit date after randomization visit is determined in relation to the date of the randomization visit (\pm the allowed visit window).
Fasting visit	X	X	X	If the participant is not fasting, the participant should be called in for a new visit within the visit window. Patients must be fasting at least 10 hours before blood sampling.
Informed consent	X			
Randomization			X	
Medical history	X			
Obesity disease assessment	X			Eleven of obesity-related health problems defined by JASSO will be utilized (Appendix 13, Section 10.13).
Adverse events and product complaints	X	X	X	At Visit 2, this activity can be performed on same day as OGTT test.
Concomitant medications	X	X	X	At Visit 2, this activity can be performed on same day as OGTT test.
Hand out diary, instruct in use			X	All training should be repeated as needed to ensure participant compliance.
Lifestyle management counseling			Х	Counselling on diet and exercise, to be performed by a dietician or equivalent qualified delegate, will include calculation of individualized energy requirement and methods to change dietary composition and amount of physical activity. The lifestyle management counseling may be delivered on a separate day from the rest of that visit's study procedures but must occur within the visit window.
Review diet and exercise goals			X	
Injection training with auto-injector demonstration device			X	
Dispense study drug			X	

Activity	Screening		Randomization	Comments
Visit number	1	2	3	
Week of treatment	-4	-2	0	
Allowable deviation (days)	NA	-7/+3	-3/+7	The visit date after randomization visit is determined in relation to the date of the randomization visit (± the allowed visit window).
Fasting visit	X	X	X	If the participant is not fasting, the participant should be called in for a new visit within the visit window. Patients must be fasting at least 10 hours before blood sampling.
Observe participant administer study drug			X	
Patient-reported outcomes measurements				
SF-36v2, acute form			X	
IWQoL-Lite-CT			X	
EQ-5D-5L			X	
Patient Global Impression of Status			X	
C-SSRS (baseline/screening version)	X			
C-SSRS (since last visit version)		X	X	At Visit 2, C-SSRS can be performed on same day as OGTT test.
PHQ-9	X		X	

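### Exclusion criterion 14 does not use the C-SSRS given at Visit 2, so a qualifying answer covering only the interval between Visits 1 and 2 triggers no mandatory exclusion

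*Protocol*

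**What the plan says.** Criterion 14 (Protocol Section 5.2) sets out which C-SSRS answers exclude a person, and when they are read: "On the Columbia-Suicide Severity Rating Scale (C-SSRS) at Visits 1 or 3, prior to randomization". The excluding answers are a yes to Question 4, a yes to Question 5, or a yes to any listed suicidal behaviour (actual, interrupted or aborted attempt, or preparatory act). Part d adds a time condition: "the ideation or behavior occurred within the past month".

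Table 1 in Section 1.3 schedules two forms during screening. "C-SSRS (baseline/screening version)" is marked at Visit 1 only. "C-SSRS (since last visit version)" is marked at Visits 2 and 3. The comment on the second form confirms that the Visit 2 assessment is intended: "At Visit 2, C-SSRS can be performed on same day as OGTT test".

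The neighbouring criteria are these. Criterion 12: "Have any lifetime history of a suicide attempt". Criterion 13 applies a PHQ-9 cut-off at Visit 1 or 3, and Table 1 schedules the PHQ-9 at exactly those two visits. Criterion 11 concerns a significant psychiatric disorder within two years. Criterion 21 turns on whether, in the investigator's view, a condition would stop the person following and completing the protocol. Section 10.4.7.12 sends anyone with these C-SSRS answers to a mental health professional.

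**The concern.** The scale is completed three times before randomization, but the entry rule reads two of those results. This would not matter if the Visit 3 form looked back over the whole of screening. Its title says that it looks back only to the previous visit, and the previous visit has its own C-SSRS. The Visit 2 form is then the only record of what happened between Visits 1 and 2, and it is the one the criterion leaves out.

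The stake is participant safety at entry. Someone who gives, during screening, an answer that would exclude at Visit 1 or Visit 3 can be randomized without breaching any criterion, because the answer was given at Visit 2. Section 8.2.5 says that participants are screened at trial entry for depression and for suicidal ideation and behaviour, so the omission runs against the plan's own purpose. No passage gives a reason for it.

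**Working it through.** There is no sample size, power or error-rate figure to reproduce. The check is a comparison of passages and day arithmetic.

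**1. Which form covers which interval** (look-back read from the form titles in Table 1)

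| Visit | C-SSRS form | Period covered | Named in criterion 14? |
|---|---|---|---|
| 1 (Week -4) | baseline/screening | before Visit 1 | yes |
| 2 (Week -2) | since last visit | Visit 1 to Visit 2 | no |
| 3 (Week 0) | since last visit | Visit 2 to Visit 3 | yes |

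The middle row is the gap.

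**2. Length of the uncovered interval.** Count days from Visit 1 = day 0. Visit 2 is nominally day 14 with a window of -7/+3 days:
- earliest 14 - 7 = day 7; latest 14 + 3 = day 17.
- As a share of the nominal 28 days: 7/28 = 25%, 14/28 = 50%, 17/28 = 61%.
- Table 1 lets the Visit 2 C-SSRS be done on the OGTT day, which may be 0 to 4 days before the visit. That can only shorten the interval.

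**3. Age of the event against the one-month condition**
- At the Visit 2 report, an event since Visit 1 is at most 17 days old. Within the scheduled windows this is always inside a month.
- At Visit 3, nominal schedule: the event lies between 28 - 14 = 14 and 28 - 0 = 28 days back, still inside a month.
- At Visit 3, with its -3/+7 window (days 25 to 35): the Visit 2 report is 25 - 17 = 8 to 35 - 7 = 28 days back, and the oldest event it could cover is 25 to 35 days back. At the late edge this passes one month by a few days.
- If windows instead run from the preceding visit (an assumption; Table 1 does not fix the anchor for screening visits), Visit 1 to Visit 3 spans 7 + 11 = 18 to 17 + 21 = 38 days.
- Screening can run longer still. Table 1 allows a late Visit 3 for MRI-PDFF re-capture, and Appendix 14 allows up to 90 days from Visit 1 in exceptional circumstances.

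**4. Does any other rule make a Visit 2 yes a mandatory exclusion?**
- Criterion 12: covers a suicide attempt, not ideation or preparatory acts.
- Criterion 13: no PHQ-9 is scheduled at Visit 2.
- Criterion 11: needs a psychiatric disorder of stated severity.
- Criterion 21: a matter of investigator opinion, tied to completing the protocol.
- Section 10.4.7.12: referral, with no effect on eligibility stated.

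None does so for Question 4, Question 5 or preparatory acts. For interrupted and aborted attempts the answer depends on how a site reads attempt in criterion 12.

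**The case against.** The strongest reply is that nothing here is a strict contradiction. A schedule may collect more than an entry rule uses, and a yes at Visit 2 is not ignored. Section 8 requires all screening evaluations to be reviewed, self-harm forms are completed at Visit 2, Section 10.4.7.12 calls for referral, and a further C-SSRS and a PHQ-9 follow at Visit 3 before randomization. This stands as far as it goes: the person is seen and referred. But review under Section 8 is review against the criteria, and referral does not exclude. Problems still present at Visit 3 are caught; those reported only for the earlier interval are not.

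Two further points stand in part. The look-back is inferred from the form's title, since the form is not in the documents. Criterion 12 does not define attempt, and criterion 14c uses that word for interrupted and aborted attempts too, so a site might apply criterion 12 to them.

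A reader might also infer more than the documents support:
- *That any suicidal ideation reported at Visit 2 slips through.* Only Questions 4 and 5 exclude at any visit; lesser ideation never does.
- *That such events are always within a month at randomization.* Step 3 shows that they may not be.
- *That admitting these participants contaminates the adverse event of special interest.* SAP Table GPHZ.4.1 counts screening up to first dose as baseline. SAP Section 4.5.2.1 requires an event to begin or worsen after that, and SAP Section 4.5.5.9 limits this topic to treatment-emergent events. The composite C-SSRS measures in SAP Section 4.5.5.9.2 count a yes at any time during the study and are less clear on this, but allocation is randomized and no bias between arms is shown.
- *That 25% to 61% is a share of participants.* It is a share of screening days; the documents give no rate of such answers.

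**Conclusion.** The point holds in a limited form. As written, criterion 14 attaches no mandatory exclusion to a yes at Visit 2 on Question 4, Question 5 or preparatory behaviour (and, unless criterion 12 is read broadly, interrupted or aborted attempts) when Visit 3 is negative. The uncovered interval is nominally 14 days, or 7 to 17 with the Visit 2 window, and the event is inside the criterion's own month when it is reported. Few participants are likely to be affected.

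The match between criterion 13 and the PHQ-9 schedule, and its absence for criterion 14, suggests an oversight, but the documents do not settle that.

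The conclusion assumes that the since-last-visit form looks back only to the preceding visit, that Visits 1 and 2 fall within their scheduled windows, and that criterion 14 is applied literally. The importance lies in safety at entry. It does not affect the efficacy analysis.

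**What to change.** Reconcile criterion 14 with the Schedule of Activities so that the entry rule and the screening C-SSRS assessments cover the same period, and state the eligibility role of the Visit 2 result. Listing every scheduled screening C-SSRS in the criterion is one example of how to do it. The questions and the one-month condition can stay as they are. If Visit 2 was left out on purpose, the protocol should say so and give the reason.

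The Visit 2 form is already collected, so no visit, form or participant burden is added. The change does need a protocol amendment with ethics approval (Section 10.1.1), and it might add a very few screen failures.

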5.3. Lifestyle Considerations

Per the Schedule of Activities (Section 1.3), participants will consult with a dietician, or equivalent qualified delegate, according to local standards, to receive lifestyle management

counseling at Weeks 0, 4, 8, and 12 during dose escalation and then at Week 24, 36, 48, 52, and 60 through 72 weeks as defined in the Schedule of Activities (Section 1.3).

Diet and exercise goals (based on JASSO guidelines) established during the lifestyle management counseling and the importance of adherence to the lifestyle component of the trial will be reinforced at each trial contact by study staff.

